We will conduct detailed interviews including demographics, drug and sexual risk behaviors, and medical history. Labs will include: HIV via 4th generation test, HBsAg, gonorrhea/chlamydia (urine, rectal, pharyngeal), syphilis, creatinine, and HCV RNA. Participants will be offered immediate FTAf at the IDEA SSP on the first encounter and will meet with the peer navigator for a medication management and adherence plan that may include on-site storage of medications and deliveries of PrEP coupled with provision of injection supplies.

If a participant becomes ineligible for PrEP during follow up based on renal function, other adverse events, or HIV infection, they will be contacted and discontinued from the study. Participants who test positive for HIV during study follow up will be linked to HIV care. Participants with chronic hepatitis B virus infection will be contacted immediately by the clinician for a discussion of the risks and benefits of FTAf in the context of chronic hepatitis B. Finally, PWID who decline study enrollment will be asked to participate in a brief survey that will include demographics, reason for declining, PrEP awareness and knowledge, and perceived HIV risk. Those who decline the study will receive \$25 cash payment for this brief, 30 minute interview.

[figure not shown]
The effectiveness of PrEP requires that it be taken every day minimizing missed doses as well as continuing PrEP over time during periods of potential HIV exposure. Follow up visits will occur at 1, 3, 6, 9 and 12 months. At each study visit participants will complete surveys about PrEP use since their last visit including semiqualitative/open-ended questions about reasons for use or non-use. We will use this combination of quantitative and qualitative data to determine individual and structural contributors to non-adherence and discontinuation of PrEP among PWID. For each study visit including baseline, participants will receive \$50 cash payment.

6) Arms and Interventions

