This single arm pilot study will assess the effectiveness of on site initiation of PrEP and followup at an SSP (fixed site or mobile exchange on outreach). The study is 1 year duration, and study visits are conducted at 0, 1, 3, 6, 9 and 12 months as outlined above. The intervention is delivery of PrEP outside of a traditional healthcare clinic. The principal medication offered will be FTAF 200/25mg tablet to be administered orally. In this study, we will offer Descovy to men and trans women due to decreased risk of side effects. If the participant is assigned female at birth, Truvada will be prescribed instead of study drug per FDA approval. **It is noted that significant risk for HIV among PWID is sexual.** The intervention will include wraparound support by the peer navigator. Study visits will be conducted either at the IDEA Exchange fixed location, or on the mobile unit in the community (e.g. homeless encampments). The fixed site and mobile unit are equipped with private rooms for medical encounters. Medical visit with a provider and phlebotomy will be provided on site.

7) Procedures Involved*

Figure 1. Conceptual Framework for *Rapid Mobile PrEP*

8) Primary Endpoints

| Patient-Level Outcomes | Definition | Implementation Construct Domain | Definition |
|--|---|---|--|
| PrEP levels at 6 month follow up (primary) | Intracellular levels of tenofovir diphosphate (TFV-DP) by dried blood spot (DBS). | Acceptability/feasibility of Rapid Initiation of PrEP | Number of PWID at risk for HIV that enter Rapid Mobile PrEP |
| Time to PrEP initiation post negative HIV | Number of days between receiving negative HIV test | Acceptability/feasibility of Rapid Initiation of PrEP | Mean time to PrEP initiation among PWID. |

| | | | |
|------------------------|---|-------------------------|---|
| rapid test (secondary) | result and initiating PrEP, by self-report | | |
| PrEP Persistence | TFV-DP levels on DBS, pill counts, medication log, appointment attendance | Barriers to persistence | Exploration of challenges to PrEP persistence |

9) Data and Specimen Banking*

For clinical data, we will use the UHealth's electronic health record, UChart, which is locked under dual authentication.

All data collected will be housed in the REDCap database system, which is locked under dual authentication by University of Miami Information Technology and then extracted for analysis by the principal investigator. Only study staff will have access to survey results.

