As for the in-depth interviews, sessions will be audio-recorded, transcribed by an external company, de-identified for analysis and stored on a password-protected computer in a secured office in the Don Soffer Clinical Research Center. Only study staff will have access to results.

10) Data Management*

Quantitative Data Analysis: Quantitative data will be analyzed using descriptive statistics and frequencies to examine the acceptability and feasibility characteristics of the PWID participants. Categorical data will be analyzed using frequency of responses and continuous variables will be analyzed using means and standard deviations. To assess barriers and facilitators to PrEP initiation (uptake), adherence, and retention, we will use Cox proportional hazard models to identify significant predictors for uptake, adherence, and retention on PrEP, and retention data will be presented as Kaplan-Meier survival plots. Multivariable models will be built to control for age, gender, race/ethnicity, insurance status, and income. Variables of association interest include: self-reported barriers to PrEP, sexual and injection risk behaviors, substance use, and social determinants of health (e.g., homelessness).

All quantitative data will be stored and managed in REDCap and all analyses will be performed using SAS statistical software (Version 9.4; SAS Institute, Cary, NC).

Qualitative Data Analysis: Qualitative data collected from the in-depth interviews will be analyzed using general inductive methodology, which allows for themes to be developed from the raw data based on a study objective/research question. A data codebook will be generated in an iterative process during transcript reading by the study team. All qualitative data analysis will be conducted using Dedoose (version 8.2.14, Sociocultural Research Consultants, Los Angeles, CA), a cross-platform software used for analyzing qualitative and mixed methods research.

IRB Study Number: 20210017

11) Risks to Subjects*

Study procedures: there is risk of discomfort to phlebotomy, but no risk above a routine sexual health visit

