Recruitment will be through the IDEA SSP participants with regular usage of SSP services (at least 1 visit per month). All PWID with a negative rapid HIV screen will be offered participation in this study. If they accept, SSP staff will refer to study research assistant for more information regarding this clinical trial. Study staff will be discrete from SSP staff to prevent possible undue influence.

Local Number of Subjects

IRB Study Number: 20210017

The proposed study aims to pilot the *Rapid Mobile PrEP* protocol for 100 PWID at risk for HIV. We will ask 50 PWID who decline to participate in a brief qualitative assessment to explore reasons for declining treatment.

19) Confidentiality

The REDCap surveys will be anonymous and do not solicit protected health information or any identifying information. If results of this survey are reported to any agency, or in journals or at scientific meetings, data will be de-identified and presented in aggregate. In addition to the research staff, the following entities may review information collected as part of this survey activity: 1) Office of Human Research Protections (OHRP), 2) University of Miami Human Subjects Research Office, and 3) professionals who may be evaluating this survey activity

The in-depth interviews audios and transcripts will be stored in a password-protected file that will be stored on University of Miami secure network. Audio will be deleted immediately after transcription.

In order to secure the data, all staff will be trained on confidentiality via the CITI program including Human Subjects Research and Good Clinical Practice

20) Provisions to Protect the Privacy Interests of Subjects

All data will be stored on the PI's password protected computer and data will only be shared via secured access Sharepoint with other members of the research team. The computer is secured by UM IT, kept in a locked office in the Soffer Clinical Research Center. Qualitative data will be transcribed and stored on the PI's computer and shared only with the research team. Audio will be deleted immediately following transcription. Copies of the informed consent with patient signature will be stored in a locked filing cabinet within the PI's keycard secured office.

21) Consent Process

Written consent will be obtained at the IDEA SSP by study staff.

(See attached consent documents for reference)

22) Process to Document Consent in Writing

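### Cox regression is named for predictors of uptake, but uptake is a yes/no outcome and the people who decline have no described time at risk; logistic regression fits the question and the data

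*Combined protocol and SAP*

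**What the plan says.** Section 10 (Data Management, Quantitative Data Analysis) applies one method to three outcomes: "we will use Cox proportional hazard models to identify significant predictors for uptake, adherence, and retention on PrEP". For uptake it gives no time origin, analysis set, censoring rule or tie method. The software is SAS 9.4. Adjustment is for age, gender, race/ethnicity, insurance status and income.

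Section 5 (Study Design) sets the acceptability result as the proportion of eligible PWID who choose to start, and promises correlates of initiation. On timing it says "Participants will be offered immediate FTAf at the IDEA SSP on the first encounter". On decliners it says "PWID who decline study enrollment will be asked to participate in a brief survey that will include demographics, reason for declining", followed by PrEP awareness and knowledge and perceived HIV risk. The visits at 1 to 12 months are for participants; no later contact with decliners is described.

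The section on the local number of subjects describes a "protocol for 100 PWID at risk for HIV" and adds: "We will ask 50 PWID who decline to participate in a brief qualitative assessment to explore reasons for declining treatment".

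Section 8 has a secondary outcome that begins "Number of days between receiving negative HIV test" and ends with starting PrEP. It is summarised as "Mean time to PrEP initiation among PWID".

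**The concern.** A Cox model compares those who have the event at a given time with those still at risk at that time, so it needs follow-up on people who have not yet started. Here the people who most clearly did not start are seen once. Entered as censored at day 0, they contribute to the day-0 risk set and to no other. Same-day starters become one large block of ties, and anyone who starts later is compared only with others who also start later.

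Correlates of initiation are a promised Aim 2 result. On this reading, an unstated software option and a recruitment quota would help decide which barriers are reported as significant.

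**Working it through.** The plan gives no effect size, power or event count for uptake, so there is no figure of its own to reproduce. From the documents come the cohort of 100, the 50 decliners, the offer at first encounter and the single decliner survey. Assumed here are two-sided alpha 0.05, one binary predictor, its prevalence, and the share of starters who start on day 0.

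**1. Tie method.** Take 100 starters, all on day 0, and 50 decliners censored on day 0. Let 60 of 75 with the predictor start, and 40 of 75 without it.

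- Breslow, one risk set: HR = (60/75)/(40/75) = 1.50. SE of log HR = sqrt(1/60 + 1/40) = 0.204, so the 95% CI is 1.01 to 2.24.
- Efron, solved numerically: HR 1.95 (1.31 to 2.92).
- Risk ratio with binomial variance: 1.50. SE = sqrt(1/60 − 1/75 + 1/40 − 1/75) = 0.122, CI 1.18 to 1.91. The Breslow SE is 0.204/0.122 = 1.67 times as large.
- Odds ratio: (60 × 35)/(40 × 15) = 3.5. SE = sqrt(1/60 + 1/15 + 1/40 + 1/35) = 0.370, CI 1.7 to 7.2.

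**2. Number of decliners.** Let the predictor be present in 50% of 100 starters and 30% of C decliners, with all starts on day 0. The Breslow HR is then [50/(50 + 0.3C)]/[50/(50 + 0.7C)] = (50 + 0.7C)/(50 + 0.3C). The odds ratio is (50 × 0.7C)/(50 × 0.3C) = 2.33 for every C.

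| Decliners surveyed | Breslow HR | Efron HR | Odds ratio |
|---|---|---|---|
| 50 | 85/65 = 1.31 | 1.56 | 2.33 |
| 100 | 120/80 = 1.50 | 1.77 | 2.33 |
| 200 | 190/110 = 1.73 | 1.96 | 2.33 |
| 400 | 330/170 = 1.94 | 2.11 | 2.33 |

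With 50 decliners, the same data give p = 0.18 (Breslow), 0.026 (Efron), 0.022 (discrete ties, HR 2.32) and 0.021 (logistic). Discrete ties with all starts on day 0 return essentially the odds ratio and remove the dependence on C.

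**3. Power.** 100 starters, 50 non-starters, predictor in 50% v 30% (OR 2.33). Late starts are spread evenly over days 1 to 30. There were 2,000 runs per setting; the discrete column is from a separate 1,000 runs.

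| Starters on day 0 | Non-starters' follow-up | Breslow | Efron | Discrete | Logistic |
|---|---|---|---|---|---|
| 100% | none | 12% | 62% | 65% | 66% |
| 80% | none | 12% | 37% | 30% | 65% |
| 50% | none | 8% | 13% | 12% | 64% |
| 20% | none | 5% | 6% | 7% | 65% |
| 80% | 30 days | 41% | 63% | – | 66% |
| 50% | 30 days | 55% | 61% | – | 64% |
| 20% | 30 days | 59% | 61% | – | 65% |

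A closed-form two-proportion calculation gives 65.1% for the logistic column.

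Under Breslow with all starts on day 0, the z statistic at the null shrinks by sqrt((n − d)/(n − 1)) = sqrt(50/149) = 0.58, and the simulated type I error is about 0%. With staggered starts and no decliner follow-up, the median Efron HR also shrinks towards 1: 1.39, 1.18 and 1.07 at 80%, 50% and 20% on day 0.

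A stronger assumed effect (OR 3) gives the same pattern at 100%, 80% and 50% on day 0 without follow-up: Breslow 37%, 22%, 9%; Efron 87%, 55%, 15%; logistic 84 to 89%.

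**4. Covariates.** Section 10 adjusts for insurance and income and lists sexual and injection risk, substance use and homelessness as variables of interest. The decliner survey in section 5 names none of these, although demographics may cover some. An adjusted model that includes decliners may lack covariates whatever the regression method.

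**The case against.** The strongest reply is that the plan never places decliners in the Cox model. Their survey is short, is called qualitative, and does not name several of the model covariates. A model of enrolled participants, who have visits to 12 months, is at least as plausible. That stands: with non-starters followed for 30 days, Efron is within a few points of logistic regression. But such a model describes timing among those who joined the study. It does not describe initiation among eligible PWID, which is how section 5 frames acceptability.

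A reader might infer three stronger claims that the documents do not support.

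- *Everyone who starts does so on day 0.* Section 5 says PrEP is offered then, and section 8 defines days to initiation and its mean, so later starts are expected. They do not rescue the model if decliners are censored at day 0; they make it worse.
- *Real predictors will be missed.* This is conditional. With Efron or discrete ties and all starts on day 0, power is close to that of logistic regression. The plan names no tie method, so Breslow cannot be assumed.
- *The fault holds whatever the comparison group.* It does not, as the rows with 30 days of follow-up show.

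A robust variance on the Breslow fit would also bring its SE to 0.122. That repairs the interval around the sample risk ratio but not the dependence of that ratio on the number of decliners surveyed.

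Logistic regression has its own condition: the odds ratio survives sampling of decliners only if being surveyed is unrelated to the predictors, and paid volunteers may not meet this.

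**Conclusion.** The concern holds in conditional form. Cox is a stated method that does not match a yes/no outcome with no described follow-up of decliners. With decliners censored at day 0, the hazard ratio varies with the tie method (1.50 v 1.95 on identical data). It also varies with the number of decliners surveyed, except with discrete ties when all starts are on day 0. Power falls well below logistic regression under Breslow ties, or under any of the three tie methods once starts are staggered. Limited to enrolled participants, Cox works but answers a narrower question.

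The power figures rest on assumed prevalences, day-0 shares and alpha. The mismatch between method and outcome does not.

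This should be fixed rather than must be fixed. Correlates of initiation are a secondary, unpowered aim of a single-arm pilot. The primary outcome, tenofovir diphosphate at 6 months, and the uptake proportion itself are unaffected.

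**What to change.** In section 10:

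- Replace Cox for uptake with logistic regression of started yes/no. Report results labelled as odds ratios with 95% CIs.
- State the analysis set: enrolled starters, enrolled non-starters and surveyed decliners. Say how the 50 decliners are chosen, and that the odds ratio assumes being surveyed is unrelated to the predictors.
- Limit adjustment to covariates collected in both groups, or add the missing items to the decliner survey.
- Take the uptake proportion from a log of all eligible PWID approached, not from the 100 and 50.
- Report time to initiation descriptively among starters, for example the shares starting the same day, within 7 days and within 30 days.
- Keep Cox and Kaplan-Meier for retention.

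The cost is a short paragraph in section 10, simpler code and, if chosen, a few survey items. The downside is that odds ratios overstate risk ratios when uptake is common, so they must not be read as risk ratios.

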Inclusion criteria for this study are: 1) over the age of 18, 2) speak either English or Spanish, 3) ability to provide informed consent, 4) currently enrolled in the SSP and have exchanged at least two times in the past three months, 5) have a negative HIV rapid test result, 6) estimated creatinine clearance > 30 ml/minute for Descovy and >60 for Truvada. Individuals will be excluded from this study if they 1) do not meet the above criteria of inclusion, 2) decline to participate, 3) test positive for HIV via rapid test, 4) are pregnant or plan on becoming pregnant 5) have symptoms acute HIV. *Any other comorbidities that at the discretion of the investigator would prevent the participant from participating in the study.*

5) Study Design

To create a sustainable protocol for dissemination of our *Rapid Mobile PrEP* initiation at future Florida SSP expansion sites (Aim 1):

Firstly, we will develop a protocol for initiation of *Rapid Mobile PrEP* at the Miami IDEA SSP site. Throughout the grant period, we will continuously update our protocol through rapid feedback and implementation of new approaches to overcome encountered problems as they arise. In addition to academic dissemination of our work, we will produce an adaptable protocol for new SSPs as they expand throughout the state. We will enroll a prospective, open-label cohort, similar to the PrEP Demonstration Project at the Miami-Dade County Health Department, assessing uptake, adherence, and retention.

Acceptability and feasibility of *Rapid Mobile PrEP* among SSP clients (Aim 2):

We will pilot test mobile PrEP at the IDEA SSP (N=100), conducting ongoing brief qualitative assessments and process improvement and developing sustainable protocol for adaptation at Florida's SSP expansion sites in geographic hotspots. We will report the proportion of eligible PWID who elect to initiate *Rapid Mobile PrEP* to understand acceptability among at-risk PWID. Likewise, we will report correlates of initiation and retention. We hypothesize that coupling PrEP services with the provision of syringes and harm reduction equipment will increase retention in this *Rapid Mobile PrEP* initiation study.

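### Section 10 promises significant predictors of three outcomes from Cox models in about 100 people, with no limit on model size or on the number of tests; the results should be reported as exploratory estimates.

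*Combined protocol and SAP*

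**What the plan says.** The combined protocol and SAP puts the analysis under 10) Data Management, Quantitative Data Analysis. For barriers and facilitators, "we will use Cox proportional hazard models to identify significant predictors for uptake, adherence, and retention on PrEP". On adjustment: "Multivariable models will be built to control for age, gender, race/ethnicity, insurance status, and income". The variables of interest are then listed as "self-reported barriers to PrEP, sexual and injection risk behaviors, substance use, and social determinants of health (e.g., homelessness", and the list is open-ended.

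The cohort size is in 5) Study Design: "We will pilot test mobile PrEP at the IDEA SSP (N=100"; the section on the local number of subjects repeats it. That section adds: "We will ask 50 PWID who decline to participate in a brief qualitative assessment to explore reasons for declining treatment". Under Study Design, the decliners' survey covers "demographics, reason for declining, PrEP awareness and knowledge, and perceived HIV risk".

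The documents do not give the expected number of events for any outcome, the number of model parameters, whether predictors enter together or singly, a selection method, a significance level, or any handling of multiple tests.

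**The concern.** A commitment to identify significant predictors treats the p-value as the decision rule. Here the rule applies to three outcomes and an unstated number of variables, and nothing controls how many false findings result. Reporting correlates of initiation and retention is a stated part of Aim 2, so this affects what the trial can conclude on that aim.

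The second worry is model size. Five adjusters use at least five parameters, and more once race/ethnicity, insurance or income has over two levels. If all predictor groups join them, a cohort of 100 may supply few events per parameter. Standard Cox intervals then tend to be too short, and sparse levels can leave a coefficient without a finite estimate.

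A smaller point: 3) Background names economic barriers as part of the problem under study, yet Section 10 names insurance and income only as variables to control for.

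**Working it through.** **Inputs from the documents.** 100 participants; three outcomes; five adjusters; four predictor groups; 50 decliners surveyed in addition. N=100 comes with no power, precision or event count, so there is no plan figure to reproduce.

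**Assumptions.** Two-sided 5% tests; 30 to 70 events as the main range (20 to 95 in the simulations); 1 to 10 predictor terms.

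**1. Number of tests.** With k independent exact 5% tests and no real effects, P(at least one false finding) = 1 - 0.95^k.
- k = 3 x 4 = 12: 1 - 0.95^12 = 46%; expected false findings 12 x 0.05 = 0.6.
- k = 3 x 10 = 30: 1 - 0.95^30 = 79%; expected 30 x 0.05 = 1.5.

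These figures contain no overfitting. Correlation between outcomes would change the probabilities but not the expected counts.

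**2. Model size.** Events per parameter = events / df. Coverage and error rates are from simulated Cox models (N=100, 800 to 2000 runs per scenario, mostly binary uncorrelated covariates, untied times, Wald intervals).

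| Adjuster + predictor terms | df | Events per parameter at 30 / 50 / 70 events | 95% interval coverage | False-positive rate per null term |
|---|---|---|---|---|
| 5 + 1 | 6 | 5.0 / 8.3 / 11.7 | 93.5-96% | about 5-6% |
| 5 + 4 | 9 | 3.3 / 5.6 / 7.8 | 93-95% | 5-7% |
| 7 + 6 | 13 | 2.3 / 3.8 / 5.4 | 92.5-93.5% | 6.5-7.5% |
| 8 + 10 | 18 | 1.7 / 2.8 / 3.9 | 91-92% | 8-9% |

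At 19 df and 30 events the ratio is 30/19 = 1.6. A separate simulation with multi-level categories (600 runs, 50 events) gave 93.5% coverage at 14 df and 88.6% at 19 df. The Monte Carlo standard error of the latter is sqrt(0.886 x 0.114 / 600) = 1.3 points, so its 95% range is 86.1 to 91.1%, at or below the low end of the table.

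**3. Which cause is larger.** Compare exact independent tests with the simulated chance of any false finding in a single model.
- 4 predictors: 1 - 0.95^4 = 18.5%; simulated 17-25%.
- 6 predictors: 1 - 0.95^6 = 26.5%; simulated 32-36%.
- 10 predictors: 1 - 0.95^10 = 40.1%; simulated 53-59%.

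Most of the risk is already there with exact tests. Backward selection at 5% does not remove it: 27-35% with 6 candidates and 48-51% with 10.

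**4. Sparse categories.** With the five adjusters in assumed ordinary categories plus one predictor (10 df), ordinary Cox estimation left a coefficient non-estimable in about 18% of simulated cohorts at 30 events and 6% at 50. With Firth penalisation the figure was 0%.

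**5. Precision.** For an assumed hazard ratio of 2 with a 50/50 split and no adjustment, power = Phi(sqrt(events x 0.25) x ln 2 - 1.96).
- 30 events: Phi(1.90 - 1.96) = 48%.
- 50 events: Phi(2.45 - 1.96) = 69%.
- Events for 80% power: (1.96 + 0.84)^2 / (0.25 x 0.4805) = 65.3, so 66.

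**Limit of the simulations.** They use untied times, whereas "Follow up visits will occur at 1, 3, 6, 9 and 12 months", so outcomes recorded at visits would be tied. Ties, correlated covariates or sparse levels could shift the figures.

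**The case against.** The strongest reply is that Section 10 does not describe one large model. It speaks of models in the plural, lists the adjusters, and names the variables of interest separately. One predictor plus five adjusters is an equally natural reading, and there coverage is close to nominal. A reader might infer that the models are overfitted and their intervals materially too narrow. The documents do not support that as fact, because neither event counts nor parameter counts are given. Even with all groups in one model, the undercoverage is mostly a few points.

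The event range is also assumed. Medication is offered at the first encounter, so uptake could approach 100 events, or 95/9 = 10.6 per parameter at 9 df with 95 events. For uptake, 100 people is not a certain ceiling either: the 50 decliners could raise it to 150, although their survey does not name insurance, income, substance use or risk behaviours. For adherence and retention, 100 is the ceiling.

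Finally, this is a single-arm pilot with a descriptive feasibility analysis, and its primary endpoint (drug level at 6 months) does not depend on these models. The expansion sites are promised an adaptable protocol; the documents do not say that the correlates will guide them.

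All of this stands, and it limits the model-size point. It does not answer the multiplicity point, which holds even with exact tests and one predictor per model. Nor does pilot status make a promise of significant predictors exploratory.

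**Conclusion.** The point holds in a limited form. Section 10 commits to "Cox proportional hazard models to identify significant predictors for uptake, adherence, and retention on PrEP" without controlling how many tests feed that list. False findings are therefore likely: 46% for at least one over 12 tests and 79% over 30, assuming independent exact 5% tests and no real effects.

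The model-size problem is conditional. If the groups enter together at 13 to 19 df with 30 to 70 events, coverage is about 91 to 94% (88.6% in one categorical scenario) and false positives run at about 6.5 to 9% per null term. If predictors enter singly, the remaining risk is non-estimable coefficients in sparse categories at low event counts, which depends on the assumed category frequencies.

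Two stronger demands are tempting but not warranted: removing race/ethnicity, insurance and income as adjusters, and a fixed cap of one parameter per ten events. The first trades modest small-sample bias for possible confounding, and nothing in the documents settles that trade. The second is a rule of thumb, and coverage at 6 df stayed close to nominal even at 5 events per parameter.

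**What to change.** Change the Quantitative Data Analysis paragraph in Section 10 as follows:

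1. Fit one predictor of interest at a time, with the five stated adjusters kept, by Firth-penalised Cox regression with profile-likelihood 95% confidence intervals.
2. Also report the estimates for insurance and income, since economic barriers are of interest. A model with the five adjusters alone would give one estimate for each.
3. Replace the aim of identifying significant predictors with reporting hazard ratios and 95% intervals for all examined variables, labelled exploratory.

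Step 3 addresses the multiplicity problem. Step 1 addresses coverage and non-estimable coefficients but does not reduce the number of tests.

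The cost is analysis-plan wording only; no data collection or sample size changes. The downside is that the study will have no list of significant predictors and no model that adjusts all predictors for one another, so overlapping effects, such as homelessness and substance use, will not be separated.
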